# 1 STUDY OVERVIEW AND PROTOCOL SUMMARY

## 1.1 Study title:

Loop-mediated isothermal amplification test development, implementation and evaluation for yaws eradication

## 1.2 Acronym:

LAMP4Yaws

## 1.3 Study design:

This study will take place in three sub-Saharan African countries known to be endemic for yaws. We aim to screen approximately 60,000 participants, of all ages. Screened participants will undergo primary clinical examination for yaws-like lesions and will be classed as either suspected yaws or negative for active yaws. A proportion of the yaws free participants ( $\approx 10\%$ ) and all those with suspected yaws ( $\approx 6000$  people) will be invited to answer a questionnaire relating to household demographics and possible risk factors for yaws. If resources allow they will also be asked to provide dried blood spots for future serological analysis of yaws and other co-endemic neglected tropical diseases. Rapid point of care (POC) serological tests will then be used to confirm the clinical yaws diagnosis in the field, to allow for recruitment into the diagnostic evaluation study. Those with suspected yaws lesions will be tested with the SD Bioline syphilis test and those who test positive will be confirmed with the Chembio Dual Path Platform Syphilis Screen and Confirm POC test (herein DPP). As some cases of yaws occur in individuals who have not yet sero-converted, in order to improve the *Treponema pallidum pertenue* (TPE) prevalence estimate accuracy, we will collect lesion samples from all individuals with a dual seropositive DPP (treponemal and non-treponemal) and a subsample of the participants (1/10) negative for the SD Bioline or the DPP (either treponemal antibodies, non-treponemal antibodies or both). Two swabs, collected simultaneously from the same lesion, will be used for the diagnostic evaluation of the *T. pallidum* and *Haemophilus ducreyi* Loop-mediated isothermal amplification (TPHD LAMP) assay. Up to three further swabs may be collected from the same or additional lesions of the participant and from individuals with non-seroreactive tests but yaws-like lesions. We will also collect swabs of asymptomatic skin and of fomites of the house from some participants with and without yaws. These additional swabs will allow us to investigate other pathogenic causes of lesions using specific nucleic acid amplification tests and next generation sequencing. We will also be able to perform supplementary laboratory analysis on swab collection and DNA extraction methodologies, investigate the role fomites may have in the transmission of TPE and *H. ducreyi* and further understand the role of *H. ducreyi* as a cause of skin ulcers. No more than five lesion

swabs will be collected from any one individual. Further to this, we will enrol people from yaws endemic communities, healthcare workers and key stakeholders into sub-studies examining knowledge, attitudes and practices in relation to yaws, skin disease, and their diagnosis.

#### **1.4 Study Sites:**

Field studies and laboratory testing will take place in three countries in West Africa: Cameroon, Cote d'Ivoire and Ghana. These countries have been selected as they have currently the highest reported incidence of yaws in Africa. Within each country, national reporting data will be used to select three districts that are highly endemic for yaws, to allow for more rapid attainment of the required number of participants with active yaws for the LAMP diagnostic evaluation.

#### **1.5 Study participants and planned sample size:**

Patients of all ages in endemic districts will be recruited into the study. In total, we plan to perform an initial clinical screen on approximately 60,000 participants of whom we expect 6,000 will present with yaws-like lesions. Of these we expect around 600 individuals will have a dual positive DPP test and will therefore be eligible for the diagnostic evaluation.

#### **1.6 Planned Study period:**

36 months

#### **1.7 Research question/Aim:**

LAMP4Yaws is a multidisciplinary study aiming to determine whether the *T. pallidum* and *H. ducreyi* Loop-mediated isothermal amplification (TPHD LAMP) test is suitable, feasible and cost-effective for use in national yaws eradication programmes and/or routine yaws surveillance. The main aim is supported by additional, linked social science and laboratory analysis that we hope will allow us to learn more about risk factors associated with disease, local transmission dynamics, other skin conditions and build in country capacity to run efficient yaws eradication campaigns.

#### **1.8 Primary objectives:**

- 1) Perform active case searching and collect household and community level data to identify risk factors associated with yaws transmission and disease.
- 2) Assess the accuracy, acceptability and feasibility of the TPHD-LAMP assay for *T. pallidum* and *H. ducreyi* diagnosis under programmatic conditions in yaws endemic areas in Ghana, Cote d'Ivoire and Cameroon to determine its suitability as a diagnostic in yaws eradication programmes.
- 3) Testing the *Treponema pallidum* macrolide resistance (TPMR)-LAMP assay in a field setting.

- 4) Establish other infectious causes of non-yaws ulcers using specific PCR tests and next generation sequencing techniques, including novel devices such as employing the Minion for nanopore sequencing.
- 5) Collect data on community, patient and healthcare worker knowledge, attitudes and practices in relation to yaws.
- 6) Determine the acceptability and feasibility and cost effectiveness of the TPHD-LAMP assay.

### **1.9 Secondary objectives:**

- 1) Build within-country capacity for future national yaws eradication campaigns.
- 2) Refine and evaluate the current TPHD-LAMP assay to enable accurate detection of macrolide resistance in a field setting.
- 3) If macrolide resistance is detected we will use whole genome sequencing to explore the evolution and transmission routes of resistant strains.
- 4) Develop an external quality assurance scheme for molecular diagnosis of yaws across endemic countries.
- 5) Collect an archive of swabs from people and fomites, which can be used to evaluate alternative methodologies for swab collection, DNA extraction, molecular testing, and investigations of bacterial transmission.
- 6) Collect an archive of dried blood spots from participants for future serological analysis to detect other neglected tropical diseases and/or previous exposure to Treponemes.
- 7) Establish which other skin conditions are commonly co-endemic in Ghana, Cote d'Ivoire and Cameroon.

## 1.11 Funding:

This study has been funded by an EDCTP grant (RIA2018D-2495)

## 1.12 Role of study funder:

The funder has not played any role in the study design.

## 2 BACKGROUND AND RATIONALE

### 2.1 Background

#### 2.1.1 Yaws

Yaws is a chronic infectious disease of the skin, bone and cartilage caused by the spirochete bacterium *Treponema pallidum* subsp. *pertenue* (TPE). TPE is closely related to the syphilis-causing bacterium *Treponema pallidum* subsp. *pallidum* but unlike syphilis, yaws primarily affects children and is generally not sexually transmitted. It is one of the World Health Organization (WHO) neglected tropical diseases (NTDs) and under the WHO's new roadmap is targeted for eradication by 2030^6. Yaws presents initially as a bacteria-rich papilloma, which if left untreated, can ulcerate. In some cases, the disease progresses to secondary yaws and it is at this stage that it can cause further skin manifestations as well as inflammation of bones and joints. In rare cases tertiary yaws develops; this is often characterised by destructive and disfiguring lesions. Untreated patients are susceptible to developing a latent infection, which can relapse, commonly within five years of the initial infection. During the latent stage of the disease there are no clinical manifestations. It is thought that for every clinical case of yaws there are six latent cases, which has serious implications for eradication programs.

#### 2.1.2 Historical and contemporary eradication strategies

Yaws was once reported to be endemic in more than 80 countries, but global prevalence was reduced by over 95% as the result of a 1950's to 60's WHO/UNICEF eradication campaign involving mass drug administration (MDA) of single dose parenteral penicillin. Most likely, a lack of resources, reduced political will and premature discontinuation of efforts led to a resurgence of yaws and the disease. A single dose of oral azithromycin has since been shown to be highly effective at treating yaws. This resulted in a revised WHO yaws eradication strategy, which consists of azithromycin MDA at the district or sub-district level, followed by active-case finding and treatment of remaining cases. Human yaws is currently known to be endemic in 14 countries, with the majority of cases reported in West Africa, South East Asia and the Pacific. Prevalence estimates are likely to be an underestimate due to a lack of systematic mapping data and under-reporting of the disease. To meet eradication targets it is essential that all endemic areas are accurately mapped to allow for targeted interventions. However, this is dependent on the availability of an accurate diagnostic method, that can be deployed in all suspected yaws-endemic districts in a standardised manner.

### **2.1.3 Diagnostics**

Accurately diagnosing yaws will be key to the success of the global eradication campaign.

Traditionally, serological tests have been the mainstay of yaws diagnosis, consisting of detection of treponemal and non-treponemal antibodies. Anti-treponemal antibodies are long-lived so are useful for indicating exposure but cannot distinguish between current and past infections, nor can they distinguish between infection with any of the *T. pallidum* subsp. *pallidum* (syphilis), *pertenue* (yaws), *endemicum* (bejel) or *T. carateum* (pinta). Non-treponemal tests are used to predict a current infection, but lack specificity. When used in conjunction non-treponemal and treponemal tests are a better indicator of a current treponemal infection, but also fail to distinguish between different species of Treponemes, and have been shown to miss early cases of yaws, which could be important for identifying resurgence of the disease after MDA.

Clinical diagnosis based on lesions alone is unreliable, often due to the presence of co-endemic ulcer-causing diseases. Recent studies using molecular tools have demonstrated only one third of yaws-like ulcers are positive for *T. pallidum*. Studies from Papua New Guinea and Solomon Islands have shown *H. ducreyi*, the causative agent of chancroid, to be responsible for a further third of these clinically-indistinguishable lesions. Often neither *T. pallidum* nor *H. ducreyi* are detected in these lesions and it is possible another infectious agent is responsible. Therefore, we will conduct further investigations to determine if other pathogens may be routinely detected that could influence the design of yaws eradication programs.

The urgent need for novel diagnostics is perhaps most essential in light of the emergence of azithromycin-resistant TPE. These strains have been shown to emerge independently, and have led to localized transmission. Highly sensitive and specific nucleic acid amplification tests (NAATs) which include tests for azithromycin resistance are available. However, these tests are often inaccessible and have limited use in the field setting. In light of this emerging macrolide resistance it is clear that more robust laboratory-based surveillance is required.

### **2.1.4 Significance and Scientific Rationale**

Improved understanding of yaws transmission and novel yaws diagnostics are urgently needed to support the WHO eradication campaign. Current WHO strategy is based on clinical case searches combined with serological point of care (POC) assays. An improved understanding of yaws epidemiology, informed by diagnostics, would help refine and improve case search approaches and contact tracing as part of eradication efforts. Given the limitations of existing diagnostics, improved diagnostic tests are needed. These tests should be designed to fulfil the WHO REASSURED criteria, i.e. allow for real-time connectivity, easy to collect specimens, be affordable, sensitive, specific, user-

friendly, rapid, equipment-free and deliverable to end users . The TPHD LAMP test (Mast Diagnostica GmbH, Germany) is a POC test that is practical to use in resource-limited areas. LAMP does not require expensive equipment, such as thermocyclers required for traditional NAATs, and the reagents have been designed to be stored lyophilised for field conditions. The TPHD LAMP test can rapidly identify an infection with *T. pallidum* or *H. ducreyi* and has been shown to have high sensitivity and specificity in the laboratory . It can also be adapted to include azithromycin resistance detection . This test may, therefore, provide a suitable solution to the problems faced by current yaws diagnostics and if accurate and feasible to use in the field, has the potential to be used by yaws eradication programs, allowing for systematic real-time detection of *T. pallidum* and *H. ducreyi*, as well as azithromycin-resistant strains.

### **3 RESEARCH AIMS AND OBJECTIVES**

[figure not shown]
LAMP4Yaws is a multidisciplinary study aiming to determine whether the TPHD LAMP test is a suitable, feasible and cost-effective diagnostic tool for yaws eradication campaigns and surveillance. The main aim is supported by additional, linked social science and laboratory analysis that will allow us to learn more about risk factors associated with disease, local transmission dynamics, other endemic skin conditions and build in country capacity to run efficient yaws eradication campaigns. This project consists of four linked sub-studies:

1. Multi-country case searches and epidemiological analysis of risk factors for yaws and other causes of yaws-like skin lesions (SECTION 4)
2. Performance evaluation of a TPHD LAMP assay compared to qPCR for the diagnosis of yaws-like lesions and optimisation of sample collection and processing (SECTION 5)
3. Use of molecular tools and next-generation sequencing to understand the aetiology of yaws-like lesions, and optimise sequencing tools for POC use (SECTION 6)
4. A health economic and social science evaluation of healthcare worker and community knowledge-attitudes and practices in relation to yaws and related diseases, and their diagnosis (SECTION 7)

By performing these four linked studies we hope to achieve a better understanding of the epidemiology of yaws in our chosen districts including identifying key risk factors and transmission dynamics, and determining the main aetiologies of lesions. The evaluation of the TPHD LAMP assay and the social science analyses will result in data that allow us to conclude if the current assay is a useful tool for routine diagnostics and use in yaws eradication programmes. An outline of each specific sub-study is given below.

#### **3.1 Overall Study Outline and recruitment**

**Figure 1:** Flow chart of participant recruitment across all three-study countries. Initially we will screen 60,000 people of whom we expect 6000 will present with yaws-like lesions. These 6000 participants, along with 6000 without clinical evidence of yaws will be invited to take part in sub-study 1, the epidemiological analysis. All participants with clinically suspected yaws will be tested with a serology POC test, with positive results being confirmed by second POC test. Those with clinical and serological evidence of yaws will be invited to participate in sub-studies 2 and 3. Additionally, some participants from studies 1-3 along with healthcare workers and key stakeholders will be invited to enrol in study 4.

\* A DPP test is considered positive only if sero-reactive for both treponemal and non-treponemal antibodies.

### 3.2 Study Sites

In each of the three countries, national reporting data will be used to select at least three districts that are highly endemic for yaws, facilitating rapid fulfilment of the sample size required number of yaws cases for the diagnostic accuracy study. The number of villages/communities selected will depend on prevalence of the disease. This exercise will be conducted with the yaws programme national coordinators in the three endemic countries.

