### 3.3 Consent and information for participants

In each site we will conduct active case finding activities in collaboration with Ministry of Health departments and National Yaws Programmes. For sub-studies 1-3, all residents in selected communities will be eligible to participate in the study. Prior to any study procedures, written informed consent will be obtained from participants or, from parents, guardians, or legal

representatives if the participant is under the age of consent. Following national recommendations informed consent will be conducted in English or French, with the assistance of a community representative translating if necessary. If a person is illiterate the study information and consent procedure will be clearly explained to them by a member of the study team or a local translator. If a translator is used they will be required to witness the informed consent procedure. Children and minors over ten years of age and under the age of consent, will also be required to give verbal assent for enrolment. If consent is not given for future research, it will be indicated under the appropriate section in the consent form. If any participants wishes to withdraw from the study at any point post-enrolment this will be indicated to study coordinator and data managers for complete elimination of that participants information. Consent forms, approved by all relevant ethical review boards, will be available in English and French, as appropriate. Individuals at each site will be consented for participation into each sub-study based on the relevant inclusion/exclusion criteria (see sections: 4.2; 5.2; 6.2; 7.2).

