## 4 SUB-STUDY 1: MULTI-COUNTRY CASE SEARCHES AND EPIDEMIOLOGICAL ANALYSIS OF RISK FACTORS FOR YAWS

### 4.1 Objectives

- 1) Determine the prevalence of active and latent yaws in each setting using combined clinical, serological and molecular tools
- 2) Identify risk factors associated with active and latent yaws
- 3) Collect a representative dried blood spot sample library for future serological testing

We will undertake integrated case searches for individuals with yaws-like lesions. We will collect baseline clinical, demographic and risk factor information from participants. Individuals with clinical evidence of yaws will be tested with point-of-care serological tests (SD Bioline and Chembio DPP) in line with standard WHO recommendations, and will have lesion samples collected which will form the sample set required for sub-studies 2 & 3. We may record the presence of other skin conditions seen.

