#### **4.6 Laboratory testing**

The dried blood spots will be used to conduct multiplex serological assays on the Luminex platform to look for antibodies to Treponemes and other infectious diseases. By measuring levels of anti-Treponemal antibodies in children we will be able to estimate the number of latent yaws cases within the community. We will choose a panel of infectious diseases that we know, or suspect, to be endemic in our populations and measure antibody responses specific to these pathogens in order to indicate exposure and seroprevalence at the individual, community and district level .

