## 11 ANTICIPATED POTENTIAL PROBLEMS

Table 5. Potential study problems and proposed solutions

Potential problem	Proposed solution
Delayed start of study activities due to delays in ethics approvals, procurement, other logistic impediments or due to the Covid-19 outbreak	

1) Work with relevant personnel/agencies, local and national authorities as needed to minimize impact on project timelines

2) If necessary, discuss with EDCTP re: adjustment of deliverables timeline

3) Streamline field collection by increasing number of fieldworkers

Insufficient sample size (for cases and/or controls), or slower than expected enrolment	

1) Work with local community leaders, health facility staff and other relevant personnel to identify and address possible causes

2) Increase number of clinical sites (within the same geographical/population area)

Adverse events and/or protocol violations	

1) Report to appropriate ethical committee and EOC

2) Prevention as appropriate through protocol amendment and/or personnel training

Loss of or damage of specimens during storage or transport	

1) Minimize risk with use of good-quality equipment, SOPs and training at sites, and use of well-established international courier

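### District-level seroprevalence is promised in 4.6, but nothing links the visited villages to the district, and unweighted blood spots would not describe even those villages

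*Combined protocol and SAP*

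**What the plan says.** - **Districts (1.4, 3.2).** In each country, "national reporting data will be used to select at least three districts that are highly endemic for yaws". Section 1.4 gives the reason: "to allow for more rapid attainment of the required number of participants with active yaws for the LAMP diagnostic evaluation".
- **Villages (3.2).** "The number of villages/communities selected will depend on prevalence of the disease". The plan does not say whether more villages are taken where yaws is common or where it is rare, or which villages are taken.
- **People (3.3).** Within a chosen village, "all residents in selected communities will be eligible to participate in the study".
- **Targets (4.1, 4.6).** Objective 1 of sub-study 1 is to "Determine the prevalence of active and latent yaws in each setting using combined clinical, serological and molecular tools"; setting is not defined. Section 4.6 is explicit about level: "in order to indicate exposure and seroprevalence at the individual, community and district level".
- **Blood spots (4.1, 4.3).** Objective 3 calls the library representative; 4.3 calls it a convenience sample. About 6,000 spots are planned, resources permitting, from half of about 12,000 enrolled (6,000 with lesions and 6,000 without).
- **Analysis (4.8).** Seroprevalence is a proportion with a 95% confidence interval. Weighting is not mentioned.
- **Adding sites (11).** Sites may be added in the same area if cases and/or controls fall short or enrolment is slow.

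**The concern.** A case search and a prevalence survey need different samples. Choosing places where cases can be found quickly suits the LAMP evaluation. A district figure needs villages that stand for the district, or weights that make them do so, and the plan has neither. Making all residents eligible does not close the gap, because the gap lies between villages and not within them.

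Section 2.1.2 calls accurate mapping of endemic areas essential for targeting interventions, and the national yaws coordinators take part in site selection. They are natural users of a figure labelled as the district's, and from the plan they could not tell a sound figure from one well off the mark.

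Even for the visited villages, the blood spots come from a group in which people with lesions are heavily over-represented, and 4.8 does not undo this.

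**Working it through.** **1. The plan's own precision (4.3).** The half-width for a simple random sample is 1.96 × √(p(1 − p)/n), with n = 6,000.
- p = 5%: 0.55 points (stated 0.5).
- p = 50%: 1.27 points (stated 1.3).

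The stated figures are therefore those of one pooled simple random sample, apart from 0.55 being cut to 0.5. With nine districts and an equal split (assumed), n = 6,000/9 ≈ 667 per district. The half-widths become 1.65 and 3.8 points, or 2.3 and 5.4 points with an assumed design effect of 2.

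**2. Does the village rule fix a direction?** District prevalence was simulated under assumptions that are not in the plan: 200 villages of 500 people, mean prevalence 1%, and 13 villages visited (20,000/3 = 6,667 screened per district; 6,667/500 ≈ 13). The case target was 600/9 ≈ 67 per district. The table shows the mean ratio of estimated to true district prevalence, by coefficient of variation (CV) between villages.

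| Village rule | CV 0.5 | CV 1.0 | CV 1.5 |
|---|---|---|---|
| Random, fixed number | 0.99 | 1.00 | 1.00 |
| Random, stop at 67 cases | 1.03 | 1.09 | 1.21 |
| Drawn in proportion to prevalence | 1.24 | 1.93 | 3.00 |
| Most reported cases (30% reported) | 1.62 | 3.10 | 4.83 |

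The result depends on which villages are taken, and the plan does not say. A figure pooled over districts can move either way. Take three districts at an assumed 0.5%, 1% and 2%, with an equal-weight mean of 3.5/3 = 1.17%.
- Village numbers proportional to prevalence: (0.25 + 1 + 4)/3.5 = 1.50%.
- Village numbers inversely proportional: 3/(2 + 1 + 0.5) = 0.86%.

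**3. The same point in algebra.** Let f be the share of the district population in visited villages, and k the ratio of prevalence elsewhere to prevalence in visited villages. The reported figure is then 1/(f + (1 − f)k) times the district's.
- f = 0.2: 5 at k = 0, 2.8 at k = 0.2, 1.7 at k = 0.5, 1 at k = 1, and 1/1.8 = 0.56 at k = 2.
- f = 0.5: 2, 1.7, 1.3, 1 and 1/1.5 = 0.67.

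Both f and k are assumptions.

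**4. Lesion mix in the blood spots.** Lesions are expected in 6,000/60,000 = 10% of those screened and in 6,000/12,000 = 50% of those enrolled. Assume that the half giving blood has the same mix as those enrolled. With seroprevalence a in people with lesions and b in people without, the unweighted figure is 0.5a + 0.5b and the weighted figure is 0.1a + 0.9b.

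| a, b (assumed) | Unweighted | Weighted | Ratio |
|---|---|---|---|
| 10%, 10% | 10% | 10% | 1.0 |
| 10%, 5% | 7.5% | 5.5% | 1.4 |
| 30%, 10% | 20% | 12% | 1.7 |
| 20%, 5% | 12.5% | 6.5% | 1.9 |

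**5. What weighting costs.** With 3,000 spots per group and the same prevalence p in both, the variance is p(1 − p)(0.1² + 0.9²)/3,000 = p(1 − p) × 0.82/3,000. This is 1.64 times the simple random value, so half-widths grow by √1.64 = 1.28. They go from 0.55 to 0.71 points at 5%, and from 1.27 to 1.62 points at 50%.

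**The case against.** The strongest reply has four parts.

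- **Direction.** Section 3.2 speaks of how many villages, not which. It fits equally well with visiting more villages where yaws is rarer, in order to reach the case target. This stands. A reader might infer that the district figure will be overstated; the documents support only that it could be.
- **Choice of districts.** A reader might also infer that picking endemic districts inflates the results. It does not bias estimates for those districts; it limits generalisation beyond them, and section 3 speaks only of the chosen districts. Nor does the plan say that the highest-reporting districts are taken: the text says highly endemic, and the phrase about highest reported incidence in 1.4 describes the countries. This stands.
- **Scope of the promise.** Setting in 4.1 may mean just the study sites, and the blood spots are conditional on resources and openly called a convenience sample. This stands in part. The district promise rests on 4.6, but there it is explicit, and it conflicts with the convenience label.
- **Added sites.** Section 11 is triggered by a shortfall of cases and/or controls or by slow enrolment, and added sites stay in the same area. This does not in itself favour case-rich villages. It does mean that the final list of sites may depend on yield, which is a reason to record it.

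None of this supplies a link from villages to district, or removes the lesion imbalance.

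**Conclusion.** The plan does not support a district-level seroprevalence. Selection is purposive, the number of villages is tied to the quantity being estimated, and no frame, draw or weight leads back to the district. The figure could be too high if case-rich villages are favoured, which is plausible in a case search but not stated. Direction and size are not established, and the multiples above only illustrate assumed inputs.

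The lesion imbalance is firmer, because 50% against 10% follows from the plan's own counts. Its effect ranges from none to about 1.9-fold over the assumed seroprevalences. It rests on the blood spots having the same lesion mix as those enrolled and on seroprevalence differing by lesion status. Renaming the estimate as that of the visited communities is therefore not enough by itself.

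The LAMP accuracy result is not affected by this point. The change should be made, at modest priority.

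**What to change.** 1. **4.6 and 4.8:** remove the district-level claim and report prevalence and seroprevalence for the visited communities, by community.
2. **4.1, objective 1:** state that each setting means the visited communities.
3. **4.1, objective 3:** replace the word representative so that it agrees with the convenience sample in 4.3.
4. **3.2:** before fieldwork, list the eligible communities in each district. Log how and when each is chosen or added, including sites added later under section 11. This record cannot be rebuilt reliably afterwards.
5. **4.8:** weight blood spot results back to the screened population by lesion status. In each community and lesion group, the weight is the number screened divided by the number giving blood. On the planned totals this is 6,000/3,000 = 2 with lesions and 54,000/3,000 = 18 without.
6. Keep case-seeking selection for the LAMP evaluation.

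**Cost.** This needs wording, a site log, screened counts by community and lesion status, and a little more analysis. The prevalence claim becomes narrower, and on the planned totals the pooled intervals widen by about 28%. Recruitment and case yield do not change.
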